### 2.3 Approach

**Overview and Timeline.** We will develop and test a novel smoking cessation treatment for state QL enrollees using cigarettes and ENDS, which will include education, SDM, and behavioral support. Phase 1 will include treatment development and refinement through delivery of the EEC to 10 dual users. In Phase 2, we will conduct a randomized controlled pilot study with 100 dual users randomized to EEC or QL treatment as usual (TAU). We will analyze results, identify further improvements, and determine if the EEC warrants a future RCT.

Task	2017		2018				2019	
	Q3	Q4	Q1	Q2	Q3	Q4	Q1	Q2
Phase 1: Treatment development and training	X	X	X					
Application development, Quality Assurance 	X	X	X					
Phase 2: Recruitment				X	X			
Phase 2: Intervention				X	X	X		
Phase 2: 3-month follow-up					X	X	X	
Analysis and dissemination							X	X

Application development is required to change existing electronic systems used to deliver QL treatment to include: (1) eligibility questions, study offer, and consent scripting and (2) EEC intervention delivery support and data elements to be collected on each call.

**2.3a Team:** [name] has completed extensive analyses on ENDS use among QL callers, identified education gaps and adaptive and maladaptive behavioral strategies for using ENDS, and collected focus group data on ENDS-related messages. [name] has considerable ENDS knowledge and has been invited to write ENDS reviews and commentaries by leading journals. He has developed treatments to encourage smokers to completely switch to ENDS, and has published studies on the impact of ENDS on smoking behaviors and beliefs. [name] is creating self-help booklets for smokers who vape as part of a separate ongoing R01, has a successful history of developing effective self-help materials, and has extensive treatment development experience. [name] has expertise in developing brief, phone-based treatments and training QCs in numerous studies. [name] is the Director of the Oklahoma Tobacco Helpline, and has extensive experience in tobacco cessation and training healthcare providers in motivational interviewing, which overlaps with tenets of SDM. Finally, [name], a senior biostatistician who has published extensively on tobacco and QLs, will oversee analyses and provide input on study design.

**2.3b Phase 1: EEC treatment development and preliminary acceptability testing.** *Theory.* Intervention development will follow behavior change program development best practices and will be based in social cognitive theory, self-determination theory, and the theory of reasoned action. Social cognitive theory is the basis for the existing QL coaching program and recognizes the reciprocal relationships of social environment, cognitions or personal factors, and behaviors. The theories of self-determination and reasoned action work well in the context of social cognitive theory and underlie the specific components chosen for the EEC: education, SDM, and tailored behavioral support. The theory of reasoned action highlights the need to change beliefs (e.g., misconceptions about ENDS or NRT) prior to changing behavioral intention or behavior and acknowledges the strength of norms or others’ viewpoints on behavior change, whereas self-determination theory is an underpinning of SDM and patient-centered care which asserts that a participant’s natural inclinations towards motivation, engagement and growth can be supported or thwarted based on their experiences within a social context, particularly with regard to autonomy, competence, and relatedness.

**4 Key Treatment Development Components.** (1) A treatment manual will be developed including educational material, the SDM paradigm for QP development (tailoring Elwyn’s model for applying SDM in clinical practice, and ENDS behavioral support guidelines (e.g., adaptive strategies to consider, maladaptive strategies to avoid). (2) Two educational booklets will be developed to be impactful, concise, and understandable at a 4th grade reading level on common indices. (3) QC training protocol and materials (see Training QCs below). (4) Treatment fidelity monitoring measures and enhancement methods will be developed, including design, training, delivery, receipt of treatment assessment, and use of skills assessment best practice strategies as described by Borrelli and colleagues. *Process.* The following resources will be utilized to

develop treatment components: (1) findings from [name] R01 to develop self-help materials for dual users, (2) published fact sheets and expert treatment recommendations, (3) needs assessment findings from [name] qualitative work and focus groups, (4) empirical literature, and (5) clinical and research experience, particularly from Drs. [name] and [name]’s previous work with this population. QL calls are not scripted. Instead, talking points are provided to guide QCs in treatment delivery and ensure fidelity, while allowing flexibility for clinical decision making, individualized care, and rapport development. [name] will create initial drafts of all components and work with Drs. [name], [name], and [name] through an iterative feedback process to prepare Phase 1 materials. Materials will then be reviewed by focus groups of experts and treatment delivery stakeholders at AWI, including QC trainers with expertise in adult learning, QC supervisors, and QCs as a means of preliminary acceptability testing; improvements will be made prior to QC training. Finally, the team will monitor ENDS-related media, research, practice guidelines, and regulations to revise educational materials as needed and prepare coaches to educate and respond to questions from participants. **Training QCs.** Four bachelors-level QL counselors (“QCs”) will be trained on the EEC intervention (15 training hours plus ongoing feedback and booster content). Training will include (1) ENDS product, safety, and regulation education, (2) participant education materials, (3) SDM model for QP development, (4) examples of potentially adaptive and maladaptive ENDS use strategies, and (4) session by session content and tailored behavioral support strategies. QCs have already received over 240 hours of tobacco cessation treatment training and receive ongoing supervision (see Resources section). EEC skill acquisition will be assessed via written pre-post tests of knowledge and skills and through simulated call role plays where process (helpfulness, warmth, empathy) and content adherence will be rated. Coaches will be trained to complete a checklist of all EEC components delivered on each call. **Phase 1 Procedures (n=10).** Recruitment, Study Offer, and Consent. New OKHL registrants who are dual users will be contacted by study staff who will screen, consent, and complete baseline measures by phone. In Phase 1, some participants may complete the initial intervention call prior to consent; this method of identifying participants reduces start up time and increases flexibility for treatment refinement. Inclusion Criteria. Participants must be eligible for a 5-call QL program, smoke any CPD (dual users may have already replaced some cigarettes with ENDS), report ENDS use in the past 30 days at registration, be willing to set a cigarette quit date in next 30 days, speak and read English, be non-pregnant and not planning pregnancy during study, ≥18 years of age, and willing to complete diaries. We will recruit equal numbers of males and females. Intervention & Data Collection. Phase 1 participants will then complete the EEC Assessment & Planning call. ENDS use will be assessed, education provided, and their QP developed or revisited using SDM. Calls will then proceed as shown in Table 1. Participants will complete diaries (described below) for a total of 5 weeks (first two weeks and the 7 days prior to 1-month, 2-months, and 3-months post-consent). Non-responders to the diary assessments (i.e., less than 5 of 7 days completed) will be contacted by a RA to complete a TLFB interview by phone. At the end of treatment (approx. 2 months post-registration), participants will complete the multimodal Outcomes Survey and a qualitative interview. Participants will receive

**Table 1. Call content: QL TAU and EEC Intervention**

Call Number	QL TAU (control)	Enhanced ENDS Coaching (EEC) Intervention
Addressed in every call	Intervention grounded in social cognitive theory and US PHS clinical guidelines. Assessment of current status and challenges. Modify medications or set new quit date if needed.	All EEC calls will include key QL TAU components PLUS behavioral support and education regarding ENDS use (if currently using). EEC educational booklets will be referenced. Additional call-specific components noted below.
1: Assessment & Planning	Program overview, assessment and planning with focus on setting a quit date, cessation medications, urge management, tobacco proofing and support. Quit Guide mailed.	(1) Assessment of ENDS use and intentions for use, (2) ENDS education, and (3) SDM on use of ENDS and FDA-approved cessation medications in QP. Tailored EEC educational booklet #1 mailed to participant.
2: Pre-quit date	Motivational enhancement, reinforce QP.	Reinforce QP including use of ENDS and/or medications.
3: Quit date	ACE model (avoid, cope, escape), social support, tobacco proofing.	Tailored EEC educational booklet #2 mailed to participant.
4: Quit date follow-up	Relapse prevention (RP), ACE.	If current using ENDS: (1) RP addressing plans for ENDS use, (2) address intentions for long-term use of ENDS.
5: Ongoing	RP, ACE, summarize and wrap up program.	Same additional content as call 4.
NRT provision	Same for both groups. All are eligible for 2-8 weeks of NRT (depending on insurance status) if they medically qualify and/or return a medical override letter from their doctor (see Human Subjects/Risks of NRT for more detail).	
NRT dosing	Typically based on CPD prior to start of dual use, but also utilizes QC judgement guided by an established dosing protocol. Strongly encourages stopping all non-NRT forms of nicotine (including ENDS) on quit date.	Participants will work with coaches using SDM to determine plans for ENDS and NRT use while quitting. NRT dosing will be adjusted if participants plan to continue ENDS use. QCs will assess potential side effects and QP adherence on every call and make needed adjustments to the QP or NRT dosing.

\$20 for completing the baseline, \$5/week for diaries with 5/7 days completed (or TLFB interview completed) plus a \$30 bonus for completing all 5 weeks, \$50 for final survey, and \$50 for qualitative interview (potential total: \$175). **Fidelity.** The research team will review all call recordings, code for treatment fidelity and collaborate with QC supervisors to review standard call quality metrics. Feedback will be provided to coaches. **Feedback from QCs.** Feedback from QCs on challenges with the EEC and recommendations for improvement, which will be used to refine the EEC prior to Phase 2. **Measures.** (Table 2.) Baseline. Standard QL registration includes demographic and tobacco use questions. Prior to randomization, participants will complete additional measures on ENDS and cessation medication use, knowledge and beliefs (questions from the empirical literature or developed to assess key misconceptions targeted by EEC education), and brief assessments of psychosocial functioning (depression, stress, anxiety). Treatment Adherence/ Engagement. Call completion, call minutes, and NRT sent from the QL are standardly captured data. Daily diaries. Participants will complete brief diary assessments on their use of ENDS, cessation medications, and traditional tobacco products, as well as cravings and an open-ended question on quit challenges (1-5 minutes to complete; procedures will be refined to facilitate completion during Phase 1 Pilot). Diaries can be completed (1) online via emailed mobile-optimized survey links or (2) via paper measures that will be returned by mail weekly. RAs will provide orientation to diary completion, and will closely track online completion and mailed surveys to provide reminders. Nonresponders (<5/7 days completed) will be contacted by a RA to complete a brief TLFB interview by phone. Multimodal Outcome Survey. The outcome survey will include measures used at Baseline (see Table 2) plus: (1) Program Satisfaction and Acceptability: assessed via a 10 Likert-rated item questionnaire (e.g., Would you recommend this to a friend?) and, for the EEC group only, several open-ended questions (e.g., what would you change about this program?) developed based on the methodology outlined by Dumas and Redish; (2) Treatment Adherence: questions will assess use of EEC educational materials (EEC only) and use of print materials (both groups); (3) SDM: the 3-item Collaborate scale will assess coach effort in helping participants understand quitting options, eliciting participant preferences, and integrating preferences in QP decision making, and (4) adverse events during treatment and specifically during ENDS or cessation medication use. Surveys will be emailed with a link for online completion, followed by multiple attempts to complete by phone, and finally a truncated paper survey will be mailed. Qualitative Interviews. After program completion, trained interviewers will conduct an interview to assess: (1) ENDS, NRT, and nicotine beliefs (relative harm, safety, long-term use), (2) quit strategies used and how and why ENDS were used during the program, (3) reactions to SDM model for QP development, and confidence in and adherence to QP, (4) use of and reactions to EEC print materials, (5) reactions to coaching calls and education from QCs, (6) why/why not callers would recommend the program and recommendations for improvement, and (7) diary completion experiences. Findings will be used to augment other data to determine readiness for Phase 2, as well as to refine the treatment and measures. **Criteria for Proceeding to Phase 2.** 8/10 participants would recommend the EEC to other ENDS users. 7/10 report improved knowledge about ENDS and NRT. 7/10 articulate QPs that include adaptive, but not maladaptive strategies. Iterative changes will be made to the EEC; if benchmarks are not met, we will recruit for Phase 1 until the EEC is ready.

Questionnaire	Baseline	Diary assessments	Outcome Survey b
Demographics (age, gender, race/ethnicity, education, chronic conditions, etc)	X a		
Smoking/Tobacco use details (time to first use, cigarettes per day, types of tobacco, last use, tobacco users at home/work)	X a	X (selected items)	X
ENDS use details (type of ENDS product, frequency of use, last use, reasons for use, nicotine content, ENDS users at home/work)	X	X (selected items)	X
Penn State E-cigarette Dependence Questionnaire 	X		X
Use of FDA-approved cessation medications	X	X	X
Knowledge and Beliefs about ENDS and FDA-approved cessation aids	X		X
Psychosocial functioning: PHQ-2 (depression),  GAD-2 (anxiety),  PSS (Stress) 	X		X
Cravings, open-ended questions on quit challenges		X	X
Program Satisfaction and Acceptability			X
Collaborate, 3-items c (SDM assessment) 			X
Engagement data (call completion, call minutes, NRT sent through QL)	Recorded by coaching application		
Adverse events (any serious adverse events are also recorded on coaching calls)		1x/ wk	X

aStandardly collected at QL enrollment. bMultimodal Outcome Survey at end of treatment (approx. 2-months post-registration) in Phase 1 and at 3 months post registration in Phase 2. c“Health issue” terminology will be edited to increase specificity to quitting smoking.

### **2.3c Phase 2: Randomized pilot to test feasibility and acceptability, and explore preliminary efficacy.**

**Design.** Pilot study with 100 ENDS and cigarette dual users randomized (1:1) to EEC intervention or QL TAU. Phase 2 will use the same EEC intervention and procedures described and refined in Phase 1 with several

exceptions described below. **Procedures.** *Recruitment, Study Offer, and Consent.* Participants who meet eligibility criteria based on standard registration questions will be asked if they would like to participate. Interested dual users will then be asked if they are willing and able to complete short daily questionnaires. Those who respond yes will be called back by a QC to complete consent, baseline measures, and be randomized to TAU or EEC. Randomization will be stratified by gender to ensure equal representation of males and females in each group. Participants will then immediately receive their first coaching call. *Inclusion Criteria.* Same as Phase 1. On average, 140 OKHL callers report ENDS use each month. Based on previously conducted studies, we estimate 40% (56) will meet other eligibility criteria, from which we expect to be able to recruit 80% (44) per month, allowing us to easily reach our  $N=100$  goal over 6 months. *EEC Intervention Protocol.* The EEC intervention will be developed and refined as described in Phase 1 and will follow the call schedule in Table 1. *QL TAU (Control).* The QL program (described in Table 1) has been proven effective and cost-effective in numerous clinical trials and evaluations for the general population of smokers. AWI's general approach for addressing ENDS during coaching calls was described above; however, our qualitative work suggested ENDS are often not discussed or only discussed briefly on calls. **Fidelity.** The research team will review call recordings and complete fidelity coding for 20% of EEC and TAU calls. Feedback will be provided to coaches weekly. Other fidelity domains will be reviewed and rated per procedures outlined by Borrelli and colleagues. **Measures.** All measures and compensation are as described in Phase 1 with three exceptions: (1) additional measures or measure changes needed based on Phase 1 work, (2) Outcomes Survey will be completed at 3-months post-registration in Phase 2 (in Phase 1, outcomes will be assessed at end of treatment), and (3) Qualitative interviews will be completed with 10 EEC participants total. In line with published recommendations, we are not including biochemical abstinence verification due to no face-to-face contact and no expectation for systematic reporting bias across groups. Moreover, the primary goal of the EEC is smoking cessation at 3 months. Participants may or may not be using ENDS at that time. ENDS use can result in salivary cotinine levels similar to cigarette smoking and that exceed standard biomarker thresholds, which limits utility for assessing smoking abstinence in this study. **Strategies to Minimize Attrition.** Our team has obtained outcome survey response rates of 80% using multiple modalities (phone, email, mail), incentives, and alternative contacts provided at baseline. [name] team has achieved diary completion rates of 59% in weeks 1 and 2 of an adaptive intervention study including ENDS devices; we aim to improve these rates with additional incentives, monitoring and reminder protocols. We will use participant retention and education strategies addressing research participation and engagement in consent materials. Call completion will be monitored and improvements made (e.g., increasing attempts) if needed.

**2.4d Statistical Analysis.** Participant baseline characteristics and program engagement will be summarized using proportions (with 95% confidence intervals (CIs)) and means (with SEs). We will use regression (and non-parametric rank sum tests) to examine primary hypotheses that, at 3-months, EEC participants will (1) have completed as many or more calls, (2) have satisfaction rates at least as high and rate QP development experiences more positively, and (3) report more accurate beliefs about ENDS, smoking, and quit medications, compared to TAU. Secondary outcome analyses will examine rates of 7-day point prevalence smoking abstinence and of ENDS and cigarette dual use. The control and EEC groups will be compared using logistic regression for binary outcomes or ANCOVA for continuous outcomes, while controlling for relevant baseline data (caller characteristics, nicotine dependence, smoking history). Diary data will be reviewed to categorize frequency and characteristics of ENDS, cessation medication, and cigarette use. We will explore correlates of outcomes based on product use reported on diaries to examine potential mechanisms that lead to smoking cessation or continued dual use of cigarettes and ENDS. Finally, we will explore potential group differences or moderators of treatment engagement and outcomes (e.g., gender, age, race/ethnicity, reasons for ENDS use).

We will address missing values multiple ways: 1) analyzing existing data (responders), 2) assuming worst case (smoking) for missing, 3) using multiple imputation, and 4) conducting sensitivity analyses with different non-responder relapse probabilities to determine how extreme values would need to be to invalidate results. For all aims, preliminary analyses will include summary statistics, cross tabulations of outcomes and baseline variables by group, and correlations. Standard regression diagnostics will be performed.

**Sample Size/Power.** Assuming 30% loss-to-follow-up, we will have 3-month outcomes for 35 per group, which aligns with Pilot/Stage I study recommendations. While this feasibility study is not powered to identify significant differences at the 5% alpha level, examination of CIs can identify outcomes or moderators worth investigation in a larger trial and inform treatment refinement, while avoiding over interpretation of effects.

**This study will test the first behavioral cessation treatment tailored to ENDS and cigarette dual users and provide currently unavailable ENDS and NRT use pattern data in relation to smoking outcomes.**

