**Phase 2:**

We are requesting a Waiver of HIPAA Authorization to identify eligible participants among enrollees in the Oklahoma Tobacco Helpline. When individuals call into the Oklahoma Tobacco Quitline (OKHL) and begin their enrollment they will be identified as eligible based on initial eligibility criteria that is collected during their standard OKHL enrollment process. Those who are identified as eligible will be read a brief study offer.

Interested and eligible participants will be screened, consented, and take a baseline questionnaire over the telephone. Participant responses will be recorded in password protected electronic systems. Because recruitment, intervention delivery, and follow-ups are all conducted over the phone,

electronically, or through mailed materials, we are not collecting a signed consent or HIPAA Authorization.

Phase 2 is a randomized pilot study where up to 130 dual users of cigarettes and e-cigarettes will be randomly assigned to receive OKHL treatment as usual or the study intervention treatment that has been tailored for users of e-cigarettes who want to quit smoking cigarettes. Our target is to have 50 callers in each group who engage in at least one session of treatment. Because this is a small sample pilot study where we want to examine the utility of the treatment for those who engage, if a caller does not complete their first treatment call after at least 5 attempts have been made to reach and complete Call 1, the participant will be withdrawn from the study and notified that they are no longer in the research study. These participants will receive coaching support from the OKHL.

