**Randomization:**

- After consent and baseline, the participant will be randomized (*see Study scripts*) into the study at which time they will be considered enrolled into the study. Randomization will be stratified by gender so that equal proportions of males and females are randomized into each treatment arm.
- Following randomization, participants will complete their first coaching call with a coach trained for the group the participant was placed in.
  - If no coach is available, participant will be called back and 5 attempts to reach participant for their Call 1 will be made. If participant is not reached after 5 attempts they will be ineligible for the study and will continue with standard OKHL services.

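### Phase 2 randomisation is stratified by gender, but SAP 2.4d does not commit to using that factor in the between-arm analysis; the cost is small and on the conservative side

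*SAP*

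**What the plan says.** **Design.** The SAP (2.3c, Design) plans a "Pilot study with 100 ENDS and cigarette dual users randomized (1:1) to EEC intervention or QL TAU". On the randomisation step, SAP 2.3c (Procedures) says: "Randomization will be stratified by gender to ensure equal representation of males and females in each group". The protocol (Phase 2, Randomization) says: "Randomization will be stratified by gender so that equal proportions of males and females are randomized into each treatment arm".

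**Recruitment by gender.** Under the Phase 1 inclusion criteria, the SAP says: "We will recruit equal numbers of males and females". SAP 2.3c carries the Phase 1 inclusion criteria over to Phase 2 without restating them. The protocol's Phase 2 eligibility list contains no limit by gender.

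**Analysis (SAP 2.4d).**
- The primary hypotheses on calls completed, on satisfaction and quit-plan ratings, and on beliefs are to be examined by regression together with rank-sum tests. That sentence names no covariates.
- After the secondary outcomes are introduced, the arms are to be compared by logistic regression or ANCOVA, "while controlling for relevant baseline data (caller characteristics, nicotine dependence, smoking history").
- Gender is named once, as an example of a group difference or moderator to be explored.
- The sample-size paragraph states that the study is not powered for significance at the 5% level and that confidence intervals will guide what is worth taking to a larger trial.

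**The concern.** A factor used to stratify randomisation normally belongs in the analysis. Stratifying removes between-arm variation due to that factor. An analysis that ignores it still counts that variation in the standard error, which is then too large whenever the factor is related to the outcome.

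Here a plain rank-sum test cannot use the stratum at all. Whether the regressions use it is left to what is later judged relevant. The pilot says it will read its results from confidence intervals, and two of its primary hypotheses ask whether the new coaching is at least as good as usual care. An interval wider than the design warrants makes that slightly harder to show. What is at stake is a modest loss of precision and an avoidable choice left open after data are seen.

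**Working it through.** **1. The plan's own figure.** From the SAP: 100 randomised 1:1, with 30% loss. 100 / 2 × (1 − 0.30) = 35 per group. This agrees with "Assuming 30% loss-to-follow-up, we will have 3-month outcomes for 35 per group" and is the analysed size used below. The protocol's target leads to the same number: "Our target is to have 50 callers in each group who engage in at least one session of treatment", and 50 × 0.70 = 35.

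**2. Interval width, linear models.** If gender explains a share R² of the outcome variance and is balanced between arms, the width without gender relative to the width with it is about 1/√(1 − R²). The documents give no R²; 2-10% is an assumed range.
- R² = 0.02: 1/√0.98 = 1.010
- R² = 0.05: 1/√0.95 = 1.026
- R² = 0.10: 1/√0.90 = 1.054

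The excess is therefore about 1-5%.

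**3. Test size and power.** A simulation used 40,000 runs, 35 per arm, a continuous outcome with within-gender SD 1, arms balanced by gender, close to 50:50, and a two-sided 5% test. The gender effects are assumptions. The assumed treatment effect of 0.67 SD is roughly what 35 per arm detects with 80% power: (1.96 + 0.84) × √(2/35) = 0.67. At 50:50, a gender effect of g SD corresponds to R² = 0.25g² / (1 + 0.25g²).

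| Gender effect (SD) | R² | Size, gender omitted | Size, gender included | Power, omitted | Power, included |
|---|---|---|---|---|---|
| 0 | 0 | 5.0% | 5.0% | 78.8% | 78.9% |
| 0.3 | 0.022 | 4.7% | 5.0% | 78.2% | 78.8% |
| 0.5 | 0.059 | 4.2% | 4.9% | 77.3% | 79.2% |
| 1.0 | 0.200 | 2.9% | 5.1% | 71.4% | 79.0% |

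Simulation error on a 5% size is √(0.05 × 0.95 / 40,000) = 0.001, or 0.1 points. With 60% women, the sizes with gender omitted are similar: 4.8%, 4.6% and 3.0% for effects of 0.3, 0.5 and 1 SD. Omission makes the test conservative, never liberal, and costs about 1-2 points of power at 0.3-0.5 SD.

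**4. What stratification delivers.** With 100 randomised 1:1 within gender, each arm receives half the women and half the men. The female shares are assumptions.
- 50% women: 25 women and 25 men per arm
- 60% women: 60/2 = 30 women and 40/2 = 20 men per arm
- 70% women: 70/2 = 35 women and 30/2 = 15 men per arm

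The two arms match at every intake. Equal numbers of men and women within an arm arise only if intake is itself equal.

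**5. Balance at analysis.** The protocol withdraws randomised callers who do not complete Call 1, and the SAP allows for 30% loss. The balance achieved at randomisation need not persist among those analysed, which is a further reason to fix the covariate in advance.

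**The case against.** **The adjustment sentence may already cover this.** It is not expressly limited to secondary outcomes. The two secondary outcomes are both rates, so its ANCOVA clause for continuous outcomes would have little to act on unless it also reached the primary ones. Gender fits naturally within caller characteristics. This is a fair reading, and it means nobody can say that the plan excludes gender from its models. But the sentence lists classes qualified by relevance, so inclusion remains a choice, and no reading of it makes a plain rank-sum test adjust.

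**The effect is small and its size is assumed.** This stands. The 1-5% figure is a linear-model result. In logistic regression, adding a prognostic covariate changes the odds ratio being estimated and generally does not shrink its standard error, so the figure does not carry over. A van Elteren test yields a p-value, not an interval; it brings the test into line with the design but does not narrow anything. The SAP also disclaims power and warns against over-interpretation.

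**A stronger reading on representation.** A reader might infer that the SAP promises a 50:50 split within each arm that it cannot deliver, because Phase 2 has no recruitment quota. The documents do not support that firmly. The protocol sentence reads naturally as balance between arms, which stratification provides. The SAP's statement on recruiting equal numbers sits within inclusion criteria that Phase 2 adopts, so the intention may carry over. What remains is that no Phase 2 text says how such an intention would be applied.

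**Conclusion.** The point holds as a small, readily corrected weakness in the analysis plan. Phase 2 stratifies by gender, and SAP 2.4d does not commit to using the stratum. The rank-sum test it states cannot use it.

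For continuous outcomes, intervals would be about 1-5% too wide if gender explains 2-10% of variance. At gender effects of 0.3-0.5 SD, a nominal 5% test would run at about 4.2-4.7%. Both ranges rest on assumed gender effects and on arms that stay balanced by gender. A reader might infer invalid tests or distorted estimates; the calculations show the opposite direction of error for the tests, and omitting a balanced stratum does not itself bias the arm difference. The equal-representation wording is a matter of clarification only.

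**What to change.** In SAP 2.4d:
- Name gender, as the randomisation stratum, as a fixed covariate in the regression, ANCOVA and logistic between-arm models, and state that this applies to primary and secondary outcomes alike.
- Replace the plain rank-sum test with a gender-stratified (van Elteren) test, taking interval estimates from the regression models.

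As a minor clarification in SAP 2.3c, word the aim of stratification as balance between arms by gender. Alternatively, if equal recruitment of men and women is meant to apply in Phase 2, say so and describe how it is applied. The protocol's Randomization sentence can stay as it is.

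The cost is SAP wording only. Gender is already collected at quitline enrolment and used to randomise, and the sample size does not change.
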